12.6 Subgroup analyses

12.6.1 Clinical and Demographic subgroups

Subgroup analyses will be performed for a) separate procedures b) separate age groups c) separate genders and d) separate racial/ethnic groups. Patients will be stratified using each classifier and the primary analyses replicated in each subgroup.

12.6.2 Patients at risk of unplanned prolonged opioid use (UPOU).

Hypothesis: Patients at moderate to high risk for UPOU, defined by score on the pain catastrophizing scale, pre-operative opioid use, and/or chronic pain will use NPPC modalities significantly less frequently than patients who are at low risk of UPOU.

Self-reported use of NPPC, expressed as a binary (Yes/No) response and assessed at 3 month post-surgical time point, will be compared between patient subgroups stratified by UPOU risk.

12.6.3 Patients who are rurally situated.

Hypothesis. Patients who are rurally situated, as defined by US Census Bureau criteria, will use NPPC modalities significantly less frequently than patients who are situated in urbanized areas and urban clusters.

Self-reported use of NPPC, expressed as a binary (Yes/No) response and assessed at 3-month post-surgical time point, will be compared across patient subgroups defined by US Census Bureau urban/rural criteria.

12.7 Supplementary Analyses

12.7.1 Moderators

In supplementary analyses we will assess whether procedure, age, sex, or race/ethnicity moderate the intervention effect. The models (1)-(5) used in the primary analysis will be expanded to include indicators for one of these subgroup classifiers, as well as the interaction with intervention status. By testing whether the interaction effect differs from zero, we can assess whether these factors moderate the intervention.

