6 STUDY DESIGN

This study will utilize a cluster randomized stepped wedge design. Clusters are defined at the level of care teams and qualifying surgical procedures, and have been randomized to one of five different tranches to implement the intervention at staggered intervals (one new cluster each wave, see diagram below).

The primary outcome of the study is a composite of patient reported pain and function at three months post-surgery. This will enable us to determine the effectiveness of a bundled NOHARM Healing after Surgery Guide + clinical decision support for promoting non-pharmacological pain management strategies to patients undergoing qualifying surgeries, which may also ultimately curb overall patient demand for opioid prescriptions in post-acute post-surgical rehab while optimizing functional recovery. Thus, our secondary outcome(s) is opioid use at the 3 month point post-operatively. This will enable us to understand the impact of our EHR-embedded decision support intervention in an era where opioid prescribing is already being constrained.

All patients receiving common, pre-defined procedures within 7 surgical practice areas at 6 Mayo Clinic locations will receive the study intervention if their surgery date coincides with the stepped wedge implementation schedule. Study locations include Mayo Clinic Rochester, Mayo Clinic Florida, and Mayo Clinic Arizona, as well as three Mayo Clinic Health System sites (Mankato, MN; La Crosse, WI; and Eau Claire, WI). Surgical practice areas will include orthopedic surgery, colorectal surgery, gyn surgery, obstetrics, pulmonary/thoracic surgery, liver and kidney transplant, and cardiac surgery. Due to variable combining of post-op unit care areas, practice size, and related considerations we have formed 22 clusters that will be randomized across 5 tranches.

Enrollment in the intervention arm of the trial will extend from March 2021 to approximately August 2023. Participating practices will be enrolled in the study from the point in time the intervention is implemented in their practice and continuing through the end of the study.

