7 SELECTION AND ENROLLMENT OF PARTICIPANTS

7.1 Inclusion Criteria

All patients 18 years of age and older undergoing qualifying surgeries at participating sites will be eligible.

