12.5 Data Analyses

Because patients are randomized in clusters, all statistical methods will account for potential correlation of measures within clusters. Such methods include cluster adjusted standard errors for t-tests and χ^2 -tests, and mixed effects models. Patient characteristics will be summarized by intervention status, and tested for difference between intervention groups; any factors which are imbalanced will be accounted for in the main analyses. Factors assessed for balance and potential inclusion in pre-specified analyses are those listed in Section 13.1.1 and all baseline measures listed in 13.1.2.

The primary and secondary outcomes will be compared between intervention groups using mixed effects generalized linear models. Each model will include an indicator for intervention group; a random intercept for cluster; cluster level factors that were used to constrain randomization; calendar time; surgery type; and any patient factors that were imbalanced across groups.

The model details for each outcome are as follows:

1. PROMIS CATs (anxiety (1°), physical function (1°), pain (1°)). These are continuous measures, collected at two time points, pre-operative and 3 months post-operative. To assess the impact of the intervention on these we will estimate three separate models. If Y_{ijt} is the measure at time $t=1,2$ of the i th patient treated by the j th cluster, then we will estimate

$$Y_{ij2} = \beta_0 + \beta_I I_{ij} + \beta_B Y_{ijo} + \beta_T T + \mathbf{B}_X \mathbf{X}_{ij} + \mathbf{B}_Z \mathbf{Z}_j + u_j + e_{ij} \quad (1)$$

where I_{ij} indicates the intervention status, T is calendar time, $u_j \sim N(0, \tau^2)$ is a cluster level random effect, X_{ij} is a vector of patient characteristics, including surgery type, Z_j is a vector of cluster characteristics used for randomization, and e_{ij} is a residual error. By testing $\beta_I = 0$ we can assess whether the intervention is associated with changes in the corresponding measure.

2. NPPC use. This is collected as a binary value for each of 14 modalities, collected at one time point, 3 months post-operative. We will sum these to create a score, and use a model similar to (1) but without a baseline value Y_{ij0} :

$$Y_{ij} = \beta_0 + \beta_I I_{ij} + \beta_T T + \mathbf{B}_X \mathbf{X}_{ij} + \mathbf{B}_Z \mathbf{Z}_j + u_j + e_{ij} \quad (2)$$

Again by testing $\beta_I = 0$ we can assess whether the intervention is associated with changes in the corresponding measure.

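### Moderators are tested one at a time, so a different intervention effect in gyn surgery and obstetrics can appear as moderation by sex or age

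*Combined protocol and SAP*

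**What the plan says.** Section 12.7.1 sets the aim: "In supplementary analyses we will assess whether procedure, age, sex, or race/ethnicity moderate the intervention effect". To do this, models (1)-(5) "will be expanded to include indicators for one of these subgroup classifiers, as well as the interaction with intervention status". A non-zero interaction is then read as evidence that the factor moderates the intervention.

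Surgery type is already in the base model of section 12.5, where the patient covariate vector "is a vector of patient characteristics, including surgery type". It has no interaction with intervention status there.

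Section 12.6.1 follows the same one-factor pattern: "Subgroup analyses will be performed for a) separate procedures b) separate age groups c) separate genders and d) separate racial/ethnic groups". The method is stated next: "Patients will be stratified using each classifier and the primary analyses replicated in each subgroup".

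Section 6 lists the practice areas: "Surgical practice areas will include orthopedic surgery, colorectal surgery, gyn surgery, obstetrics, pulmonary/thoracic surgery, liver and kidney transplant, and cardiac surgery". It also says: "Clusters are defined at the level of care teams and qualifying surgical procedures".

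On age, section 7.1 says only: "All patients 18 years of age and older undergoing qualifying surgeries at participating sites will be eligible". The documents give no sex or age distribution by procedure.

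**The concern.** Sex and procedure are tied together by the choice of practice areas, not by chance. Gyn surgery and obstetrics contribute women and essentially no men. Constrained randomization (12.2.1) balances the allocation of clusters to waves and does nothing to separate sex from procedure.

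A main effect of surgery type adjusts the level of the outcome. It cannot absorb a difference between procedures in the size of the intervention effect. When sex x intervention is the only interaction in the model, it picks up part of any such difference. The plan treats a difference between procedures as possible, because procedure is one of the moderators it tests. The same mechanism applies to age if obstetric patients are younger than the rest, which is reasonable but not stated.

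At stake is a statement that women, or younger patients, benefit less or more when neither factor matters within any procedure.

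**Working it through.** **Plan's own figure.** The documents give none for the moderator analyses. The nearest is the detectable main effect of 0.048-0.055 SD in section 12.2, used here only as a scale for plausible gaps. It cannot be reproduced exactly, because alpha, power and cluster sizes are not stated.

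**Inputs from the documents.** 22 clusters in 5 waves (12.2); 114,000 patients planned (1.5); surgery type as main effect only (12.5); one interaction per model (12.7.1).

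**Assumptions, not in the documents.**
- k = 3, 6 or 9 of 22 equal clusters are women-only.
- Women are half of the patients elsewhere.
- There are six periods.
- 57,000 (half of those planned) or all 114,000 have the outcome.
- The residual SD is 1.
- The true effect in women-only procedures differs from the rest by d, with no true moderation by sex.

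**Step 1: rough size in the stratified analysis (12.6.1).** With f = k/22 and q = 0.5, the share of women who come from women-only procedures is f / (f + (1 - f)q).
- k = 3: 0.136 / (0.136 + 0.432) = 0.24
- k = 6: 0.273 / (0.273 + 0.364) = 0.43
- k = 9: 0.409 / (0.409 + 0.295) = 0.58

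If patients count about equally, the female-minus-male difference in effect is about that share times d. For d = 0.10 SD it is about 0.024, 0.043 and 0.058 SD.

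**Step 2: sex interaction model (12.7.1).** Weighted least squares was run on cluster-period-sex cells, averaged over random allocations to waves. The model had cluster effects (standing in for the random intercept and surgery-type main effects), period effects, intervention, sex and sex x intervention. The rejection rate is Φ(z - 1.96) + Φ(-z - 1.96), with z = bias / SE.

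| Women-only clusters | Share of d in sex term | SE at 57,000 / 114,000 | d = 0.025 | d = 0.05 | d = 0.10 |
|---|---|---|---|---|---|
| 3 | 0.19 | 0.0172 / 0.0121 | 6% / 7% | 9% / 12% | 20% / 35% |
| 6 | 0.34 | 0.0179 / 0.0127 | 8% / 10% | 16% / 27% | 49% / 78% |
| 9 | 0.48 | 0.0191 / 0.0135 | 10% / 14% | 24% / 43% | 71% / 94% |

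Example: k = 6, d = 0.10, 114,000 analysed. The bias is 0.0346, z = 0.0346 / 0.0127 = 2.72, and the rejection rate is about Φ(0.76) = 78%. With d = 0 the rate is 5% in every row.

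**Step 3: add women-only procedure x intervention.** The sex interaction returns to 0 and its rejection rate to 5%. Its SE at 114,000 becomes 0.0128, 0.0139 and 0.0155, which is 5%, 10% and 15% larger. Using seven separate practice-area interactions gave the same correction, with an SE 5-14% larger.

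**Step 4: separate check with simulated outcomes** (ICC 0.037, 60 to 200 runs per setting). With 14% and 27% of clusters women-only, about 19% and 34% of the gap passed into the sex term. For d = 0.10 the sex interaction was falsely significant in 35% and 72% of runs at 114,000, and in 22% and 51% at 57,000. Across d = 0.05 and 0.10 it was 7-17% at 20,000.

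Age tested alone, with younger patients assumed in the women-only clusters, gave 7% and 25% for d = 0.05 and 38% and 72% for d = 0.10 at 114,000. The joint model gave 3-8% for age across settings. The age figures are indicative only, because the age mix is assumed.

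**The case against.** Four arguments on the other side carry weight.

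- **Gap size.** A gap of 0.10 SD is about twice the stated detectable main effect. If the average effect is near 0.05 SD, a gap that large would mean little or no effect, or a reversed one, in one group. Nothing in the documents suggests that gyn or obstetric patients respond differently, and at 0.025 SD the error rate is 6-14%. This stands, and it is why the result is given by gap.
- **Procedure is tested too.** A gap large enough to distort the sex term would also be examined under its own heading in 12.6.1 and 12.7.1. That makes an unqualified misreading less likely. It leaves the sex or age coefficient uncorrected, and the plan has no rule for reading the two results together.
- **Estimand.** A one-factor interaction validly describes whether the average effect differs between women and men in this surgical population. That is true, and the result can be kept for that purpose. It does not show that sex itself moderates the effect.
- **Cluster make-up.** Section 6 says that clusters were formed partly by combining post-operative units, so gyn or obstetric patients may share clusters with others. The women-only share is therefore uncertain.

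A reader might infer that a procedure difference will be reported as moderation by sex. The documents do not support that: it needs a gap that lines up with sex mix, only part of it passes into the sex term, and significance depends on gap, share and number analysed. Nor does this check show that race/ethnicity is affected; no calculation was made for it.

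**Conclusion.** The one-at-a-time moderator models cannot separate sex, or age, from procedure. If the effect in gyn surgery and obstetrics differs from that in other areas, about 20-50% of the gap can appear as moderation by sex when 3 to 9 of 22 clusters are women-only. The false-positive rate across 57,000-114,000 analysed is near nominal at 0.025 SD, roughly 10-40% at 0.05 SD and 20-95% at 0.10 SD. With no gap there is no bias.

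The mechanism follows from the text of 12.5 and 12.7.1. The size rests on the assumed gap, women-only share and number analysed. The age part rests further on obstetric patients being younger, and its size is less certain because the plan uses age groups and gives no age mix.

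A reader might also infer that the trial's main results are at risk. They are not: these analyses are supplementary, and the primary and secondary effect estimates are unaffected. This is a cheap improvement.

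**What to change.** In 12.7.1, keep practice area x intervention in the sex and age-group moderator models, and base any moderation claim on the sex or age interaction from that joint model. Present the one-at-a-time interaction as a description only.

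In 12.6.1, also report the sex subgroups without gyn surgery and obstetrics.

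The cost is analysis-plan wording, with no new data. The standard error of the sex interaction rises by about 5-15% in the cases computed, because single-sex procedures no longer inform it.

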1.5 Sample Size and Population

All Mayo Clinic patients receiving one of the surgical procedures included in the NOHARM study will be enrolled in the NOHARM trial. Based on surgical volumes from 2018 and the number of patients required for sufficient statistical power, we plan to enroll 114,000 patients into the NOHARM trial.

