12.2 Sample Size and Randomization

Using pain data for 6,261 patients with these procedures at six sites, we estimated the intra-cluster correlation coefficient (ICC) for the pain score to be modest $\rho = 0.037$. To assess minimal detectable effects, we simulated a large number of randomizations and estimated the detectable effect for each. Specifically, for $P = 1, \dots, 5000$ permutations, the 22 clusters were randomly assigned to 5 waves. For each permutation, the closed form solution of Harrison et al (2019) was used to estimate $SE(Q)$ (derived from the formula of Hussey, Hughes (2008)) for true effect Q . We used the values $\sigma^2 = 1$ and $\tau^2 = 0.488$ for the within and between variance components so that detectable effects would be in SDs, and assumed ICC would be 0.037. Over the 5,000 permutations, the detectable effect ranged between 0.048SD and 0.055SD.

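### Age as a moderator is tested through undefined age groups; a continuous age-by-intervention term with a spline is a better test if the gradient is roughly linear, though the gain may be small at full enrolment

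*Combined protocol and SAP*

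**What the plan says.** Section 12.7.1 (Moderators) states that "we will assess whether procedure, age, sex, or race/ethnicity moderate the intervention effect". The method is to take models (1) to (5), which "will be expanded to include indicators for one of these subgroup classifiers, as well as the interaction with intervention status", and to test whether the interaction differs from zero.

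The classifiers are those of section 12.6.1, where age appears as "separate age groups" and where "Patients will be stratified using each classifier and the primary analyses replicated in each subgroup". Read together, age enters the moderator test as a set of group indicators. Neither section gives the number of groups, the cut-points or a reason for grouping.

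Section 13.1.1 lists age without bands, and section 13.1 says all data are extracted programmatically from the health record. Continuous age is therefore a reasonable inference, though it is not stated. Eligibility covers "All patients 18 years of age and older undergoing qualifying surgeries", with no upper limit. For another covariate the plan does consider both forms: in model (3) of section 12.5, day after surgery is entered first as continuous and then as categorical.

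**The concern.** Indicators suit procedure, sex and race/ethnicity, which are categories. For age they assume that the intervention effect is flat within each group and jumps at each cut. Two groups discard the variation in age within each half; more groups keep more of it but spend degrees of freedom. If the effect changes roughly linearly with age, both lose power against a single age-by-intervention slope.

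An age gradient is plausible here. Sections 7.3 and 8.4 say that patients who cannot use the portal-based guide are less exposed, and Appendix B describes a workbook for patients without internet access or ease with technology. The planned test could miss such a gradient. With no cuts fixed in advance, its result also depends on a choice that could be made after the data are seen.

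**Working it through.** **The plan's own figure.** Section 12.2 gives a detectable effect of 0.048 to 0.055 SD, for the main effect only. It cannot be reproduced exactly, because alpha, power and cluster-period sizes are not stated. With 22 clusters, 5 waves, 6 periods, ICC 0.037 and two-sided 5%, the Hussey-Hughes variance gives 0.030 to 0.034 SD at 80% power and 0.034 to 0.039 SD at 90% if all 114,000 are analysed. About 57,000 analysed at 90% power gives 0.048 to 0.055 SD. The point does not depend on this figure, but 57,000 is a useful second value for the number analysed.

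**Inputs.** From the documents: planned enrolment of 114,000 (section 1.5); 22 clusters and 5 waves (section 12.2); age from 18 (section 7.1). Assumed, because the documents are silent: two-sided alpha 0.05; moderation linear in age; age normal or uniform; two to five equal-sized groups; power of the continuous test set at 80% or 90%.

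**Step 1: continuous test.** The non-centrality of the 1-df test is λ = (1.960 + z)².
- 80% power: (1.960 + 0.842)² = 7.85
- 90% power: (1.960 + 1.282)² = 10.51

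**Step 2: grouped test.** With k groups, λ is multiplied by R, the share of age variance lying between groups. Power comes from the non-central chi-square with k − 1 df. For uniform age R = 1 − 1/k²; for a median split of normal age R = 2/π = 0.637. Worked case, normal age and two groups: 7.85 × 0.637 = 5.00, √5.00 = 2.236, power = Φ(2.236 − 1.960) = 60.9%.

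| Groups (df) | R, normal / uniform | Power when continuous = 80%, normal / uniform | Power when continuous = 90%, normal / uniform |
|---|---|---|---|
| 2 (1) | 0.637 / 0.750 | 60.9% / 67.9% | 73.4% / 80.2% |
| 3 (2) | 0.793 / 0.889 | 60.1% / 65.4% | 73.6% / 78.7% |
| 4 (3) | 0.861 / 0.938 | 57.3% / 61.4% | 71.3% / 75.4% |
| 5 (4) | 0.897 / 0.960 | 54.3% / 57.5% | 68.7% / 72.0% |

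The loss is 12.1 to 25.7 points at the 80% benchmark and 9.8 to 21.3 at 90%. A cut at 65, with 20% of patients aged about 31, brings the latter to about 22. An unbalanced 80/20 split loses 30 to 31 points at the 80% benchmark.

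**Step 3: this trial's scale, PROMIS outcomes.** With the outcome in SD units and half the patients exposed, the slope per SD of age has SE = 1/√(N × 0.25). For a slope of 0.033 SD per SD of age and normal age:

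| N analysed | λ = 0.033² × N × 0.25 | Continuous | 2 to 5 groups | Loss (points) |
|---|---|---|---|---|
| 33,000 | 8.98 | 85.0% | 60.8% to 66.7% | 18 to 24 |
| 57,000 | 15.5 | 97.6% | 86.4% to 89.1% | 8 to 11 |
| 114,000 | 31.0 | 99.98% | 99.3% to 99.6% | under 1 |

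This SE ignores clustering. A simulation of individual patients in a stepped wedge with 22 clusters, 5 waves, 6 periods, cluster and period effects and 33,000 patients (600 replicates) gave 86% for continuous age against 66%, 67% and 64% for 2, 3 and 4 groups, in line with the first row.

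At the full 114,000, the slope detectable with 80% power is 2.802/√28,500 = 0.0166 SD per SD of age, about a third of the plan's 0.048 to 0.055 SD. At 0.02 SD the continuous test has 92.2% and the grouped tests 72.7% to 77.3%.

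**Step 4: a rarer binary outcome.** Assume 3% daily opioid use at 3 months and an interaction odds ratio of 1.10 per SD of age, with all 114,000 analysed. Then λ = (ln 1.10)² × 114,000 × 0.03 × 0.97 × 0.25 = 7.53, or about 78% power. That is close to the 80% benchmark, so losses of about that size return.

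**Step 5: other shapes.** Take normal age and effects sized so that the correctly specified test has 80% power.
- Step at the median: median split 80%, linear term 61%, tertiles 52%, quintiles 49%.
- Symmetric U-shape: linear term 5%, median split 5%, quintiles about 30%.

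**The case against.** The strongest reply is that the size of the loss is not a property of this trial. The documents give no interaction effect, alpha, power, age distribution or number of groups, and 12 to 25 points arises only because the continuous test is set at 80% power. At the planned enrolment, the PROMIS outcomes show that loss only for gradients near 0.02 SD per SD of age or smaller. This stands, and the figure must carry its conditions. It does not remove the point: fewer patients may be analysed than enrolled, since the PROMIS scores depend on questionnaire response, and 12.7.1 also covers the count and binary models.

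A second reply is that a linear term wins under linear moderation by construction. A reader might infer from the Step 2 table that no grouping can match continuous age. The documents do not support that, because they say nothing about the shape: a cut at a true step does better, and a U-shape defeats the linear slope. This also stands, and is why a spline with a reporting rule has to accompany the linear term.

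A third reply is that age and procedure are likely to be associated, since section 6 includes obstetrics, cardiac and orthopedic surgery. A pooled age slope could partly reflect differences between procedures. That is fair, and applies to grouped age as well.

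**Conclusion.** The point holds as a cheap improvement to a supplementary analysis. The plan tests age moderation with indicators for groups it does not define, and a continuous term with a spline is the better default. Under roughly linear moderation, grouping costs about 12 to 25 points of power for two to five reasonably balanced groups when the continuous test has 80% power, and about 10 to 22 at 90%. It costs under 1 point for the PROMIS outcomes with all 114,000 analysed and a gradient of at least 0.033 SD per SD of age. All of these rest on an assumed alpha, age distribution and linear shape.

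Two stronger readings should be avoided. One might take the 12 to 25 points as the loss this trial will suffer; the documents fix none of the quantities needed to say so. One might also think the trial's main conclusion is weakened; section 12.7 is headed as supplementary, and neither the primary comparison nor the sample size depends on it.

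**What to change.** In section 12.7.1:
- Test age moderation by adding centred continuous age and its product with intervention status (1 df) to models (1) to (5).
- Pre-specify a restricted cubic spline version of the age-by-intervention term, with the rule that the spline result is reported as the shape of the effect if the test of non-linearity is significant.
- Report the intervention effect with its confidence interval across the age range.
- Add a sensitivity analysis that also includes procedure by intervention.
- Keep indicators for procedure, sex and race/ethnicity.

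In section 12.6.1, keep age groups for display only, with cut-points stated in advance.

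The cost is a sentence or two of wording in each section, with no new data, patients or procedures. The downside is that the 1-df test assumes a roughly linear gradient, which the spline term is there to cover.
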